#### Adverse Events

All adverse events will be summarized for the following 3 study periods separately, and include the specified AEs:

• Screening Period: Include the AEs of which the onset date is before the start of the study device placement.

• Treatment Period: Include (a) the AEs of which onset date is on or after the first day of the study device and on or prior to five days after the last device treatment day.

• Follow-up Period: Include (a) the AEs of which onset date is more than 30 days after the last device placement; OR (b) the AEs of which onset date is during the treatment period with the end date is more than 30 days after the last dose day or is unresolved and the follow up intensity is worse than the initial intensity.

For each AE recorded, the term entered by the investigator describing the event (the "verbatim term") will be assigned to a standardized term (the "preferred term") based on the Medical Dictionary for Regulatory Activities (MedDRA) dictionary. Within this dictionary, all preferred terms are grouped into categories known as "system organ class" terms or "super class" terms (SCT). All data displays of AE will be performed using the preferred terms and super-class terms (also referred as Body System).

For each treatment group, the frequency of each AE preferred term will be defined as the number of patients reporting at least one occurrence of the event. The incidence rate will be calculated as the frequency count divided by the total number of patients in the population and treatment group specified. Each table will also present the overall number of patients experiencing at least one AE and the total number of adverse events reported.

In the summary table of AEs by intensity, if a patient has more than one occurrence of an event, the event with the most severe intensity will be counted. If the intensity of an adverse event is missing, then the AE will be included only in the total number of events columns, and not in the count of patients with the event by intensity. In the summary table of AEs by relationship to trial treatment, if a patient has more than one occurrence of an event, the most closely related event will be counted. If the relationship of an adverse event is missing, then the AE will be included only in the total number of events columns, and not in the count of patients with the event by relationship.

The "listing of patients who prematurely withdraw due to adverse events" will include all AEs (not only the events leading to withdrawal) which were reported by the patients. Expected adverse events that are not serious will be reported on the Continuing Review Progress Report. Continuing Review will be performed on a 12-

month cycle, starting at the time of the protocol's initial approval. More frequent progress reports will be submitted at the request of the IRB.

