#### **DESIGN AND METHODS**

The study will recruit a total of 50 subjects and will take place in a well-established outpatient treatment center (Brightview). Brightview is a private addiction treatment center located in Cincinnati, Ohio. The site PI at Brightview will be [name] [name] (MD, ABIM, ABAM DABPM), a board-certified physician in addiction medicine. [name] (PhD) will be a Co-investigator. The volume of patients treated for opioid use disorder (OUD) at this facility is sufficient for patient recruitment in this study. [name] will be responsible for patient recruitment and overseeing the entire project at Brightview. He will monitor the health of all patients in the study per standard clinical practice. [name] will be responsible for patient recruitment as well and monitor protocol adherence as well as supervise data collection, entry, and analysis.

This study will involve a double-blind, randomized, controlled trial with active BRIDGE or sham device (Figure 3). The sham device will be identical in appearance to the active device but will have no electrical current. Both providers and patients will be blinded to treatment allocation throughout the study. Participants will be 18 years or older who speak English and meet criteria for opioid use disorder based on the Diagnostic and Statistical Manual of Mental Disorders-5. Patients going through acute opioid withdrawal will be assessed for the severity of opioid withdrawal using the Clinical Opioid Withdrawal Scale (COWS). Additional demographic data will be collected at presentation including age, sex, duration of opioid misuse, types of medications or illicit drugs used as well as the presence of other medical conditions. After the severity of opioid withdrawal is established (COWS score  $\geq 10$ ), subjects will be randomized in blinded fashion. Once the patient is consented, a visual analog scale (VAS) for pain and an opioid craving scale (OCS) will be completed. Baseline cognitive function will be measured with the Stroop test using the CNS Vital Signs (CNSVS) in-office neurocognitive testing software https://www.cnsvs.com/index.html. This instrument measures executive function. The test takes approximately

4 minutes to administer and will be performed at the same intervals as COWS score, pain and craving assessments before and after device placement.

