
Overall, the study will have very little deviation from the current standard of practice to treat substance use disorder (SUD), with the exception of the first hour of medical management which will be effected without

buprenorphine or symptom control medications, and the second hour during which symptom control medications will not be used. Current standard of practice in the clinical setting is to give the first dose of buprenorphine on Day 1 after initial screening, followed by a second or third dose prior to discharge home. Patients will be sent home and monitored as outpatients and asked to return to clinic within 2-5 days. The current study will not deviate from clinical practice after Day 1 with the exception of having either the BRIDGE device or sham device for 5 days. The device will be removed at the clinic visit on Day 5 and disposed of in a sharps container. If the patient cannot come back on day 5, they will be instructed to remove the device at home and bring it back at the next clinic appointment for proper disposal.

#### Figure 3

If at any time the patient wishes to discontinue the BRIDGE device and receive standard treatment for opioid withdrawal outside the study, he/she will be allowed to do so.

The study will involve the use of the NSS-2 BRIDGE device, an ambulatory, neurological device which consists of a battery powered, externally affixed generator with 4 wire leads: 1 double needle electrode lead and 3 single point electrode needle leads (Figure 4). The device delivers low voltage (3.2V) stimulation in alternating frequencies for a total of 5 days (around the clock). The arrays are designed to produce a field effect. The leads will be placed percutaneously in the external ear with the help of a transilluminator to visualize the neurovascular bundles. Three electrodes will be placed on the ventral aspect and one on the dorsal aspect of the ear. The electrodes will be taped and secured behind the ear next to the generator itself which is secured to the skin with adhesive. The placement of the devices is within standard of care by properly trained medical providers or physician extenders.

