#### Subject recruitment and enrollment

Subjects presenting to the outpatient clinic at Brightview health will be identified by the attending physician and the patient will be approached for inclusion in the study by the research coordinator if they meet criteria. The principal investigator, a co-investigator or research coordinator will introduce the study to the patient during the initial clinic visit and will explain the details and purpose of the study during an informed consent discussion and obtain consent. Once the patient had enough time to consider participation, understand the risks and benefits and agree to participate, he/she will sign informed consent and HIPAA documents.

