#### Power Calculation for primary aim (difference in COWS scores between active and sham device).

We hypothesize that compared to sham treatment, the improvement in COWS due to the BRIDGE device will be significantly higher than the sham. Similarly, pain and craving as measured by the VAS and OCS will be reduced. Patients with the active BRIDGE device will have improved memory and executive function compared to sham as assessed by CNSVS.

The primary outcome is comparison of change from baseline of the COWS scores between active and sham device at one hour. The data will be analyzed as a randomized, placebo-controlled trial with an interim analysis when 24 patients are completed at a P< 0.001. We will compare the bridge device and sham using a two sided t-test of the change of COWS at one hour form baseline. Using the sample size software Pass 15 with 25 subjects in each group we will have at least 90% power at an alpha of 0.049 to detect a difference in the COWS at one hour between treatment and sham of at least .94 standard deviations(SD), In the withdrawal study we had a SD of ~6, and so if we have a similar variability we will be able to detect a difference of approximately 5.7 (1). In the paper, we found a difference of > 12, so even allowing for a placebo effect we should have adequate power.

Period	Baseline	(1-hour after BRIDGE)	(1-hour after BUP)	Post- MAT	Post- MAT	Post- MAT	Post- MAT
Contact	Clinic	Clinic	Clinic	Phone	Phone	Phone	Clinic
Project Day	1	1	1	2	3	4	5
Informed Consent	Х						
Demographics and Medical History	Х						
Prior and Concomitant Medications	Х						х
Vital Signs, height, weight and BMI	х						
Physical Examination	Х						
Placement of BRIDGE Device or sham	Х						
COWS scores	Х	х	Х	х			х
VAS pain and craving scale	Х	х	Х	Х	х	Х	Х
Neurocognitive assessment	Х	x					Х
First dose of Buprenorphine		Х					

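### The treatment period for adverse events opens on the calendar day of device placement rather than at placement, so any event recorded with onset earlier that day enters the treatment-period tables

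*Combined protocol and SAP*

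**What the plan says.** The Adverse Events section asks for separate summaries in three periods.

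- **Screening:** "Include the AEs of which the onset date is before the start of the study device placement".
- **Treatment, lower bound:** "Include (a) the AEs of which onset date is on or after the first day of the study device".
- **Treatment, upper bound:** "on or prior to five days after the last device treatment day".

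The schedule table, printed under Power Calculation, lists "Informed Consent" and "Placement of BRIDGE Device or sham" in the same column (Baseline, Project Day 1) and shows no earlier screening visit. Other sections agree. Under Subject recruitment and enrollment, staff "will introduce the study to the patient during the initial clinic visit". The first Data Management section describes clinic practice as being to "give the first dose of buprenorphine on Day 1 after initial screening".

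Participants have symptoms when they arrive. Design and Methods states: "Patients going through acute opioid withdrawal will be assessed for the severity of opioid withdrawal". Entry requires a COWS score of at least 10.

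Two statements of scope differ. Safety Analysis describes safety assessment as covering adverse events judged related to the device, deaths and study-specific concerns. Adverse Events summarises all events, keeps a pre-device period and tabulates by relationship to treatment.

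**The concern.** The two boundaries are tied to different things: screening ends at a procedure, while treatment begins on a calendar day. They agree only if nothing can be recorded on the placement day before placement. Here the whole pre-device part of the study falls on that day.

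The document gives no treatment-emergent definition, no onset-time requirement and no rule that an existing symptom must worsen to count in the treatment period. A worsening condition appears only in the follow-up definition. Several items that COWS scores, such as nausea, anxiety, sweating and tremor, could be coded as ordinary adverse event terms.

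The counting rule adds to this. A patient counts once per term, so someone with nausea before the device and new nausea after it contributes the same as someone with the first episode only. The intensity table takes the most severe occurrence, which could be the earlier one. At stake is whether the by-arm treatment-period incidence describes what happened after the device was placed.

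**Working it through.** The plan states no figure on this point, so there is none to reproduce. The check has two parts.

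**1. Applying the period rules.** Placement is on Day 1 (schedule). The clock time of placement does not affect the result.

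| Onset of event | Screening rule read by date | Screening rule read by clock time | Treatment rule |
|---|---|---|---|
| Day before placement | in | in | out |
| Day 1, before placement | out | in | in |
| Day 1, after placement | out | out | in |
| Day 2 | out | out | in |

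Only the second row is a problem. Such an event is in treatment alone under the date reading and in both periods under the clock-time reading. When consent and placement share a day, no event arising between them can be in screening alone.

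**2. Effect on incidence.** Let q be the share of each arm with a Day 1 pre-placement event of a given term, and p the true post-placement rate. Assume the two are independent. Because each patient counts once per term:

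- observed rate = 1 − (1 − q)(1 − p) = p + q(1 − p)
- observed risk difference = (1 − q)(p₁ − p₀)

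The documents give no value for q, p₁ or p₀. For illustration only, assume p₁ = 20% and p₀ = 5%, a true difference of 15 points and a ratio of 4.0:

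| Assumed q | Observed rates | Difference | Ratio |
|---|---|---|---|
| 0% | 20% vs 5% | 15 points | 4.0 |
| 10% | 28% vs 14.5% | 13.5 points | 1.9 |
| 20% | 36% vs 24% | 12 points | 1.5 |
| 40% | 52% vs 43% | 9 points | 1.2 |

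For the last row: 1 − 0.60 × 0.80 = 0.52, 1 − 0.60 × 0.95 = 0.43, difference 0.09, ratio 0.52/0.43 = 1.2.

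Without independence, the factor (1 − q) applies to the difference among patients who had no pre-placement event, which need not equal the overall difference.

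**After the fix.** With the treatment period starting at the recorded placement time, a new event in the second row goes to screening only. The other rows do not change.

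**The case against.** The strongest reply is that few such events may ever reach the tables.

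- Withdrawal is the condition under treatment and is captured by the baseline COWS. Nothing says that entry symptoms are also entered as adverse events, and the scope in Safety Analysis would exclude them, since a symptom that began before the device cannot be related to it. This stands as a limit on size. It does not settle the matter, because Adverse Events summarises all events and keeps a period for those arising before placement.
- The screening wording shows an intent to keep pre-placement events out of treatment. That is a fair reading of intent, but the treatment rule as written still captures them.
- Other outputs help. Both safety sections call for summaries at each assessment time, and the Day 1 efficacy assessments fall before placement and one and two hours after it. The relationship table should show pre-device events as unrelated. Both reduce the harm, although the plan does not say how events map to assessment times.
- Electrode-site and adhesive effects, which make up most of the listed risks, cannot occur before placement and are not diluted.
- Safety summaries are descriptive, so no test or decision rule depends on these tables.

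A reader might infer that every participant's entry symptoms will fill the treatment-period tables, or that the tables will hide device harms. The documents support neither. Symptoms dated to an earlier day go to screening, the share with same-day onset is not given, and the outputs above leave other routes to a device signal.

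**Conclusion.** The concern holds in a limited form. The period definitions misplace any adverse event recorded with onset on the placement day but before placement, under either reading of the screening rule. They also overlap if that rule is read by clock time. This follows from the text and the schedule alone.

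The consequence is conditional. To the extent that such events are recorded, treatment-period incidence is inflated and the between-arm difference is diluted by (1 − q), given independence. The value of q is unknown and could be close to zero if entry symptoms are not recorded as adverse events. The illustrated ratios rest on assumed rates and should not be read as estimates for this trial.

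It would be wrong to infer a bias towards one arm. Randomisation makes the misplaced events similar in both arms on average. The efficacy analysis is not affected.

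**What to change.** 1. Record a clock time of onset for Day 1 adverse events, and the time of device placement.
2. Define screening as onset before the recorded placement time. Define treatment as onset, or worsening of an existing event, at or after that time. The two periods then do not overlap.
3. Reconcile Safety Analysis with Adverse Events on which events are in scope, and state whether withdrawal symptoms present at entry are recorded as adverse events.
4. Optionally, state that the assessment-time summaries will show separately the hour between placement and the first buprenorphine dose. By the protocol's own schedule, that hour has device exposure without buprenorphine or symptom-control medication.

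The cost is an onset-time field and a few sentences of plan wording. The downside is that site staff must note a clock time for Day 1 events. The field should be in place before data collection, because onset times are hard to recover afterwards.

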#### Serious Adverse Events

The PI, within 24 hours, will report all serious adverse events occurring in any enrolled subjects to the IRB. Unexpected (but not serious) adverse events occurring in enrolled subjects which, in the opinion of the PI, are possibly related to participation in the study will be reported by the PI within 5 working days to the IRB. Enrollment will be discontinued after reaching 50 subjects.

#### Safety Monitoring Plan

All procedures will be performed by trained professionals within the standard of care under continuous medical supervision while in the outpatient clinic. Potential side effects will be documented as noted above. COWS score ratings will be filled out by nursing staff or provider as per standard of care. All patients will be carefully monitored. If any serious harm or discomfort is identified by the subjects or the study personnel, the treatment will be discontinued. Any patient with worsening or no improvement in symptoms who has a device placed during the study will be able to drop out at any time and receive standard of care medical therapy. The skin of the external ear will be carefully monitored for signs of irritation or infection. All patients will be given the option to have an active device at the end of the 5 day study period at no cost.

Safety Analysis Plan

There are no dangerous interventions related to this study.

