#### Unblinding

Unblinding (or unmasking) patient's treatment assignment is only done when knowledge of the blinded treatment is necessary, for the treatment of an adverse event. Where possible patient will remain on trial and where medically feasible on assigned treatment. For all unblinding if possible, any assessors of subsequent outcomes will remain blinded. Record will be kept on unblinding and patients will be excluded from per protocol analysis but not the intent to treat analysis.

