#### **Data Collected**

All data collected will be entered into a Redcap database for analysis. All collected data will be de-identified and samples will only have a unique identifier that will link the unique identifier with the patient's name.

Results of the COWS and pain VAS scores, OCS and CNSVS assessments at the respective time points will be tabulated and analyzed.

Upon completion of each patient's treatment with the device (sham or active), patients will be asked if they thought they had an active or inactive device. They will also be asked to respond to the questions: Do you want an active, functioning device to be placed prior to going home today (yes/no)? and on a 7 point Likert scale: 1) "How useful do you think the BRIDGE Device was for you overall in your treatment?" 2) "What is your impression of the effectiveness of the BRIDGE Device to treat your symptoms of withdrawal?" 3) "How satisfied are you and how the BRIDGE device worked for you?" and 4) "How likely are you to use the device again if you have symptoms of withdrawal?" Results will be tabulated and analyzed descriptively.

Analysis will also include differences in dosing of buprenorphine as well as usage of other symptom control medications and continued engagement in recovery treatment at 5- and 30-days post-device placement. If subject does not return to clinic at the 5- and 30-day scheduled appointment as dictated by clinic standard practice, a phone call will be made to assess whether the patient is still engaged in a recovery program.

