### DATA MANAGEMENT

#### GENERAL CONSIDERATIONS FOR DATA ANALYSES

In general, for demographics, baseline disease characteristics, type of opioid misused, and all safety data, continuous variables will be summarized using descriptive statistics including N, mean, median, standard deviation (SD), minimum, and maximum. For all the efficacy parameters (e.g. COWS, VAS, OCS and CNSV experience with the device, continued engagement in recovery program) the descriptive statistics will include N, mean median, standard error (SE), minimum and maximum or percentage and exact Clopper Pearson 95% confidence interval.

**Definition of analysis population** Intent-to-treat (ITT) Population The intent-to-treat (ITT) population will include every subject who is randomized to a treatment assignment (BRIDGE or Sham). The ITT population will be the primary population for all efficacy analyses and will be the basis of all sensitivity analysis.

Patients who received study medication different from that to which they are randomized will be included in the group to which they are randomized. All data will be analyzed by randomized treatment group.

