#### Secondary efficacy analysis

As a secondary analysis we will examine the change over time of the COWS, pain VAS scores, OCS and CNSVS between groups using a mixed-effects model repeated measures (MMRM) analysis incorporating treatment period data up to 3 months. The effects in the model will include the baseline score, treatment groups, visit, treatment-by-visit interaction and baseline-by-visit interaction. Visit week will be treated as the repeated variable within a patient. Patient, treatment, and visit will be treated as class variables. Unstructured covariance matrix will be used initially, and additional types (e.g., auto- regression, Toeplitz, CS, etc.) will be tried to assess the robustness of the unstructured matrix. Comparison between treatments will be based on contrasts of least square treatment means at each week of interest. Based on the analysis above, least square means, standard errors, and 95% confidence intervals (CI) of treatment difference will be reported for the two groups.

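### For patients who choose to stop the device or do not improve, the protocol describes only leaving the study and does not commit to Day 2 to Day 5 assessments afterwards

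*Combined protocol and SAP*

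**What the plan says.** Three passages deal with stopping the device.

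- First Data Management section: "If at any time the patient wishes to discontinue the BRIDGE device and receive standard treatment for opioid withdrawal outside the study", this is allowed.
- Safety Monitoring Plan, on patients whose symptoms worsen or do not improve: they "will be able to drop out at any time and receive standard of care medical therapy".
- Safety Monitoring Plan, one sentence earlier, on harm: "If any serious harm or discomfort is identified by the subjects or the study personnel, the treatment will be discontinued". Nothing is said here about leaving the study.

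The Unblinding section does separate trial participation from treatment, but only for unblinded patients: "Where possible patient will remain on trial and where medically feasible on assigned treatment".

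On analysis, General Considerations states: "The ITT population will be the primary population for all efficacy analyses". The later COWS, pain, craving and cognition scores are to be compared "using a mixed-effects model repeated measures (MMRM) analysis incorporating treatment period data up to 3 months". The Missing data section generally assumes missing at random, specifies multiple imputation for items, and adds a descriptive summary by dropout cohort.

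The end-of-treatment questions in Data Collected are placed at completion of each patient's "treatment with the device (sham or active), patients will be asked if they thought they had an active or inactive device", followed by the four ratings. The Efficacy Information list puts the questionnaire at the end of the study period and the allocation guess at the end of five days of treatment.

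**The concern.** Two of the three stopping routes, the ones a patient takes by choice or for lack of benefit, are worded as exits from the study. No section says that scheduled assessments go on after the device comes off. Site staff who follow the wording could reasonably stop collecting.

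This matters because one exit route is defined by poor response. If the device works, more sham patients may take it; if the active device is poorly tolerated, more active patients may. Either way, the patients still measured on Days 2 to 5 would be a selected group, and the selection could differ by arm. Aim 2 makes a claim about pain and craving over the 4 to 5 days after placement, so these scores serve a stated aim.

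The end-of-treatment questions have a related problem. A patient who leaves on Day 2 has no clearly scheduled moment to give the ratings or the allocation guess, so the check on blinding and the satisfaction results would come mainly from completers.

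**Working it through.** **1. What is collected after stopping, outcome by outcome**

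| Outcome | Timing after Day 1 | Needs the device in place? | Stated for patients who stop? |
|---|---|---|---|
| Pain, craving | Days 2 to 5, clinic or phone (Day 5 in clinic) | No | Not stated |
| COWS | Days 2 and 5 | No, but it includes observed signs | Not stated |
| Cognition | Day 5, clinic | No | Not stated |
| Medication log | Ongoing | No | Not stated |
| Engagement in treatment | 5 and 30 days, with a call to non-returners | No | Covered by the call, which asks only about engagement |
| Ratings, allocation guess | Completion of device treatment, or end of 5 days | No | Unclear |

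The gap is therefore a missing commitment. The text nowhere says that collection ends.

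**2. The plan's own power figure**

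Inputs (Power Calculation): 25 per group, two-sided alpha 0.049, difference 0.94 SD, SD about 6.

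Noncentrality = 0.94 / √(2/25) = 3.323, with 48 degrees of freedom and critical t = 2.020. Power is 90.1%, which agrees with the stated 90% or more. The difference detectable with exactly 90% power is 0.938 SD. In COWS points, 0.94 × 6 = 5.64, which the plan gives as approximately 5.7.

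This figure is for the one-hour endpoint. The plan makes no power claim for Day 5.

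**3. Illustration: loss of precision on a Day 5 comparison**

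Assumptions, none from the documents: equal loss in both arms, a two-sample t-test at alpha 0.049, and patients per arm = 25 × (1 − loss), rounded down.

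| Assumed loss | Per arm | Power at 0.94 SD | Detectable at 90% power |
|---|---|---|---|
| 0% | 25 | 90.1% | 0.938 SD |
| 10% | 22 | 85.9% | 1.003 SD |
| 20% | 20 | 82.3% | 1.055 SD |
| 30% | 17 | 75.4% | 1.150 SD |
| 40% | 15 | 69.7% | 1.230 SD |

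At alpha 0.05 the detectable effects at 25 and 20 per arm are 0.936 and 1.052 SD, so the rise at 20% loss is from about 0.94 to about 1.05 SD at either level.

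**4. Illustration: bias from unequal stopping**

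Let p be the share of an arm that stops and g the number of points by which stoppers would score worse than stayers. The mean over everyone is the stayers' mean plus p × g, so the observed mean looks better by p × g. The shift in the between-arm difference is (p in sham − p in active) × g.

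Assume 30% in sham, 10% in active, and g of 3 to 6 COWS points:

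- (0.30 − 0.10) × 3 = 0.6 points
- (0.30 − 0.10) × 6 = 1.2 points

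Both run against the device; the sign reverses if more active patients stop. These are shifts in observed-case means. A mixed model would remove part of the shift to the extent that earlier scores predict stopping.

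**The case against.** The case against has real force, and several stronger readings that a reader might infer do not hold.

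- **That outcomes are definitely not collected after stopping.** This turns silence into a rule. The harm sentence stops treatment without mentioning exit, the Unblinding section separates the two ideas, and the pain and craving reassessments in the first Data Management section are not conditional on wearing the device. Its discontinuation sentence can also be read as an ordinary right to withdraw. What stands is that no section makes the commitment, and the two voluntary routes point the other way.
- **That the all-randomized analysis cannot be carried out.** It can. A mixed model includes every randomized patient with at least one post-baseline score. The plan also investigates causes of missingness by logistic regression and CART, summarizes dropout cohorts, and lists withdrawals by reason. What stands is that the result relies on missing at random, and no analysis departing from that assumption is named.
- **That the trial's main result is at risk.** The primary endpoint is at one hour, so only exits within that hour matter.
- **That the bias is about 1.8 COWS points.** This comes from assuming that the stoppers are exactly the worst 10% (active) and 30% (sham) of a normal distribution. The mean shifts are 0.1755/0.90 = 0.195 SD and 0.3477/0.70 = 0.497 SD; the difference of 0.30 SD, times 6, is 1.8. Neither the split nor the worst-case selection has a source, and the SD of 6 is used for the one-hour power calculation. The Background reports a 97% reduction by day 5 in the earlier device study, so Day 5 scores may lie near the floor. COWS also includes signs such as pupil size and piloerection, so phone contact would not simply recover it.
- **That the 37.5% dropout in the Background predicts stopping here.** It is an upper figure for leaving therapy within a month in another study. It is not a rate of device stopping, and patients who abandon treatment altogether will not be retained by protocol wording.
- **That stoppers never answer the end-of-treatment questions.** Completion of device treatment could include early completion, and these items are only analysed descriptively. The two sections leave the timing ambiguous.

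**Conclusion.** The point holds as a gap affecting secondary outcomes. For patients who choose to stop or do not improve, the text describes only leaving, and nothing commits the trial to Day 2 to Day 5 assessments afterwards. Since leaving is linked to poor response, the later all-randomized comparisons would depend on an untested missing-at-random assumption, and the ratings and allocation guess would come mainly from completers.

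The size is unknown because the documents give no stop rate. Under an assumed 20% loss per arm, the precision cost is moderate. Bias requires unequal and outcome-related stopping, which the exit wording makes plausible but does not establish; its direction depends on which arm stops more.

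This is a change the sponsor should make, because scores not taken on Days 2 to 5 cannot be collected later. It does not undermine the primary analysis.

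**What to change.** In the first Data Management section and the Safety Monitoring Plan, distinguish stopping the device from withdrawing consent for follow-up, and record the date and reason of stopping. Unless consent is withdrawn:

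- continue pain and craving scores through Day 5, in clinic or by phone;
- take COWS and cognition at the scheduled clinic visits that the patient attends;
- keep the medication log and the existing 5- and 30-day engagement contact;
- ask the four ratings and the allocation guess at the time of stopping, and align Data Collected and the Efficacy Information list on this;
- analyse all these data by randomized group.

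Clinical care after stopping stays as it is.

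The cost is protocol and consent wording plus a few phone contacts of a kind already planned. The downside is that later scores in stoppers also reflect the care they moved to, so the comparison estimates the effect of assignment regardless of stopping; the analysis section should say so. Some COWS and cognition scores will still be missing when patients do not attend.
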